**7.3 Sample Size**

The sample size will be 130 subjects per group, which is the maximum affordable sample size. This sample size will have a varying ability to detect differences between the groups depending on the proportions. For example, a two-group  $\chi^2$  test with a 0.050 two-sided significance level will have 80% power to detect the difference between a Smaller proportion,  $\pi_1$ , of 0.500 and a Larger proportion,  $\pi_2$ , of 0.670 when the sample size in each group is 130. Additional cases, assuming the same significance level, power, and sample size are shown in the following figure.

**Two group Chi-square test of equal proportions (equal n's)**

Very few or no dropouts are expected.

#### 7.4 Randomization

Subjects will be randomized to one of two treatments in a 1:1 ratio, receiving either the Test lens or the Control lens for the duration of the study. Within each site and overall, the number of subjects randomized to each treatment will be approximately balanced.

#### 7.5 Study Populations

Subject eyes will be included in all summaries under the treatment that they actually received. Analyses of safety data will include all dispensed subjects. All other summaries will include all eligible, dispensed subjects.

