#### **4.8 Masking/Unmasking**

Both the Investigator and the subjects will be masked to the study treatment. An unmasked designee at each site will be responsible for dispensing study products to the subjects according to the randomization schedule. The randomization schedule will be produced by the Sponsor statistician not otherwise involved in the study until after the database is locked.

Randomization will be completed by the unmasked designee by providing each subject's treatment assignment after the subject has been assigned a subject number (i.e., randomized). The subjects will be assigned randomization numbers sequentially as they are enrolled. The unmasked designee will open the blister packs by removing the foil out of the subject's sight (subject MUST insert lenses). The unmasked designee is also responsible for maintaining study lens inventory, randomization schedule and the Product Accountability Log in a masked fashion.

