### **5.2.7 Product Dispensing Only Visit**

If a subject is seen for resupply or replacement of study materials and the subject is not experiencing any problems, a complete exam is not required. If any assessment is performed, then an Unscheduled Visit Form must be completed instead of a Product Dispensing Only Form.

If study lenses are dispensed, collect the following information and record in the Product Dispensing Only e-CRF Form and Product Accountability Log (if applicable):

- visit date
- subject ID number
- subject initials
- primary reason for lens replacement
- dispensed lens sphere power, quantity, type, and lot number

*NOTE: All worn, unworn, dispensed, non-dispensed study lenses are to be returned as directed with the materials provided. Worn lenses will be returned DRY in lens cases.*

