#### Secondary Effectiveness Endpoints

- Lens performance survey (100 point scales) questions.

Study ROC2-17-014 - Protocol

- Comfort upon insertion
- Overall comfort
- Comfort at end of day

Secondary Safety Endpoints

- The proportion of subjects with any slit lamp findings grade 2 or greater at any time.

[figure not shown]
Hypotheses

The following hypotheses will be tested for each question in the take home performance questionnaire at each week.

1. The null hypothesis is that the proportion of subjects providing a response in the top three categories is equal between the treatment groups.
2. The alternative hypothesis is that the proportion of subjects providing a response in the top three categories is not equal between the treatment groups.

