#### 7.6 Statistical Analysis

Primary and secondary analyses will be performed on all eligible, dispensed eyes (completed and discontinued eyes pooled) for efficacy endpoints and for all dispensed eyes (completed and discontinued eyes pooled) for safety endpoints.

Questionnaire responses to the take home questionnaire will be summarized using categorical summary statistics by treatment and week. The proportion of subjects providing a response in the top three categories will be compared between treatments using chi-square tests by week. A Fisher's exact test will be used instead of a chi-square test when any cell in the contingency table has an expected count less than five.

Comfort related lens performance survey question results will be summarized using continuous summary statistics by treatment group and visit. Two-sided two-sample t-tests will be used to compare the treatment groups by visit.

The proportion of subjects with any slit lamp findings grade 2 or greater will be summarized categorically by treatment group and visit. Two-sided Fisher's exact tests will be used to compare the groups by visit.

Missing data will not be imputed.

There will be no adjustments for multiple comparisons.

There are no planned interim analyses.

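### Effectiveness is grouped by lens received rather than lens randomized, and a subject who receives both lens types has no defined arm

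*Combined protocol and SAP*

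**What the plan says.** **Grouping rule.** Section 7.5 sets one rule for everything: "Subject eyes will be included in all summaries under the treatment that they actually received". Safety uses all dispensed subjects. For the rest, "All other summaries will include all eligible, dispensed subjects".

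**Analysis.** Section 7.6 repeats these sets: "Primary and secondary analyses will be performed on all eligible, dispensed eyes (completed and discontinued eyes pooled) for efficacy endpoints". It names no as-randomized analysis, either as the main analysis or as a sensitivity analysis.

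**Design.** Section 7.4 states "Subjects will be randomized to one of two treatments in a 1:1 ratio", each subject "receiving either the Test lens or the Control lens for the duration of the study". The null hypothesis in Section 7.2 is that "the proportion of subjects providing a response in the top three categories is equal between the treatment groups". The unit there is the subject, whereas Sections 7.5 and 7.6 speak of eyes.

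**Dispensing.** Under Section 4.8, "Randomization will be completed by the unmasked designee by providing each subject's treatment assignment". Section 5.2.2 has that designee dispense one pair. Lenses can be replaced at an Unscheduled Visit (5.2.5.2), where lens type is recorded again, and at a Product Dispensing Only Visit (5.2.7), which records "dispensed lens sphere power, quantity, type, and lot number".

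**After an error.** Receiving the wrong lens type is not among the listed discontinuation reasons in Section 3.3.3, although the discretionary list there is open-ended. Section 5.5 allows subjects with deviations to continue unless the deviation puts them at risk or their condition requires discontinuation.

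**The concern.** Grouping by lens received is customary for safety. For a two-group effectiveness test it gives up what randomization provides, namely that the groups compared are those formed by chance. There are two separate gaps.

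1. **Moved subjects.** A subject who is given the wrong lens type at first dispensing, with no later correction, counts in the other arm as if allocated there. Grouped as randomized, that subject would only dilute the contrast. Grouped as received, the subject changes the composition of both arms.

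2. **Mixed exposure.** A wrong-type replacement, or a different type in each eye, means that the subject has received both lenses. The take-home survey gives one response per subject per week, and the rule for eyes cannot place that response. For a mid-study replacement, the lens received could mean the first lens, the lens worn longest, or the lens worn in the week being tested. With no stated rule, the choice would be made after data exist.

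Both gaps bear on the comparison that Section 7.2 ranks as the most important in the study.

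**Working it through.** **Inputs.** From Section 7.3: 130 per arm, proportions 0.500 and 0.670, two-sided alpha 0.05, power 80%. The document gives no rate of lens-type errors, so the number of affected subjects, k, is assumed.

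**1. The plan's own figure.** Without continuity correction, power = Φ{[d√n − z√(2p̄q̄)] / √(p₁q₁ + p₂q₂)}, where d = 0.17, n = 130, p̄ = 0.585 and z = 1.96.

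- d√n = 0.17 × 11.402 = 1.938
- z√(2 × 0.585 × 0.415) = 1.96 × 0.697 = 1.366
- √(0.2500 + 0.2211) = 0.686
- Power = Φ(0.573 / 0.686) = Φ(0.834) = 79.8%

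This reproduces the stated 80%.

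**2. Shift from grouping as received, no true difference.** Take 50% response in both arms, so 65 of 130 respond in each. Suppose k subjects randomized to one arm are counted in the other, and all are non-responders. The proportions become 65/(130 − k) and 65/(130 + k).

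| k (assumed) | Losing arm | Gaining arm | False difference |
|---|---|---|---|
| 0 | 50.0% | 50.0% | 0 |
| 1 | 65/129 = 50.4% | 65/131 = 49.6% | 0.8 points |
| 3 | 65/127 = 51.2% | 65/133 = 48.9% | 2.3 points |
| 5 | 65/125 = 52.0% | 65/135 = 48.1% | 3.8 points |
| 13 | 65/117 = 55.6% | 65/143 = 45.5% | 10.1 points |

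The last row is 10% of an arm and marks the far end of the range. For scale, the standard error of the difference at 50% response is √(2 × 0.25 / 130) = 6.2 points.

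**3. The same move at the Section 7.3 proportions.** Move three non-responders from the lower to the higher arm. The proportions become 65/127 = 51.2% and (0.67 × 130)/133 = 87.1/133 = 65.5%. The difference falls from 17.0 to 14.3 points, a shift of about 2.7.

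**4. Power under grouping as received.** With arms of 130 − k and 130 + k, nominal power is 79.8% at k = 1 and 79.5% at k = 13. The cost is possible bias, not power.

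**5. Cost of grouping as randomized.** Let k subjects in each arm wear the wrong lens throughout and respond at the rate of the lens worn. The proportions become 0.50 + 0.17k/130 and 0.67 − 0.17k/130.

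| k per arm (assumed) | Difference | Power |
|---|---|---|
| 0 | 17.0 points | 79.8% |
| 1 | 16.7 points | 78.5% |
| 3 | 16.2 points | 75.9% |
| 5 | 15.7 points | 73.1% |
| 13 | 13.6 points | 60.6% |

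**The case against.** The strongest reply is that such errors should be rare and would be seen. One pair is dispensed (5.2.2), no replacement is scheduled (3.2), and the same pair is re-inserted at two weeks (5.2.3). Accountability records (4.7), monitoring of accountability (8.2) and documentation of all deviations (5.5) should bring errors to light. Section 7.2 also says that the primary endpoints are not pass/fail. All of this stands, and it limits the expected impact. It does not supply the missing rule for mixed exposure, and it equally means that grouping as randomized would cost little.

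Four stronger readings are tempting, but the document does not support them:

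- **Every dispensing or replacement error moves a subject.** A wrong power or lot leaves the arm unchanged. A wrong-type replacement creates mixed exposure rather than a clean move. Only an uncorrected wrong type at first dispensing moves a subject.
- **Stock-outs would lead to substitution of the other brand.** Section 5.2.1(f) has sites order lenses and schedule dispensing for another day. Section 5.2.2 requires the subject's lenses to have arrived first, and Section 4.9 gives a reorder route.
- **The unmasked designee might switch lenses selectively.** Section 4.8 requires dispensing by the schedule, and no take-home response exists at first dispensing. Nothing suggests a motive, and the replacement sections do not say who dispenses.
- **Each switched subject could shift the difference by 1.5 points, and three by 4.6.** These are extremes: 2 × 1/130 = 1.5 and 6/130 = 4.6. They need response rates near 0% or 100%, or equal numbers switched in each direction with opposite responses. They should not be set against 0.50 versus 0.67.

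**Conclusion.** The point holds in a limited form. The primary effectiveness comparison is as-received by an explicit rule, with no as-randomized analysis beside it, and a subject who receives both lens types cannot be placed in an arm.

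The likely effect is small. If all moved subjects are non-responders moving the same way, the distortion at 50% response is about 0.8 points for one and 2.3 for three, or about 2.7 for three at the Section 7.3 proportions. These counts are assumptions, and a mix of responders and non-responders would shift the difference less. With no lens-type error, the results are identical under either grouping.

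The case for changing the plan rests on the rule itself and on how little the change costs. It does not rest on evidence that errors will occur or be selective.

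**What to change.** Replace the grouping sentence in Section 7.5 with wording such as:

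> Effectiveness summaries and tests include eligible, dispensed subjects under the lens to which they were randomized, including any subject who received both lens types. Safety summaries use the lens actually received; subjects who received both types are listed under each lens with dates of wear. The number of lens-type errors at dispensing or replacement is reported by arm.

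As-received effectiveness can be kept as a sensitivity analysis if wanted.

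The cost is a few sentences. Lens type is already recorded at the Dispensing, Unscheduled and Product Dispensing Only visits, so no new data are needed. The downside is slight dilution when a subject wears the wrong lens: power of about 78.5% rather than 79.8% with one such subject per arm.

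The change does not by itself produce a full intent-to-treat set. Effectiveness would still be restricted to eligible, dispensed subjects, and under Section 5.2.2 a subject can be exited as non-dispensed for lens fit after the assigned lenses have been inserted.

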#### 7.6 Statistical Analysis

Primary and secondary analyses will be performed on all eligible, dispensed eyes (completed and discontinued eyes pooled) for efficacy endpoints and for all dispensed eyes (completed and discontinued eyes pooled) for safety endpoints.

Questionnaire responses to the take home questionnaire will be summarized using categorical summary statistics by treatment and week. The proportion of subjects providing a response in the top three categories will be compared between treatments using chi-square tests by week. A Fisher's exact test will be used instead of a chi-square test when any cell in the contingency table has an expected count less than five.

Comfort related lens performance survey question results will be summarized using continuous summary statistics by treatment group and visit. Two-sided two-sample t-tests will be used to compare the treatment groups by visit.

The proportion of subjects with any slit lamp findings grade 2 or greater will be summarized categorically by treatment group and visit. Two-sided Fisher's exact tests will be used to compare the groups by visit.

Missing data will not be imputed.

There will be no adjustments for multiple comparisons.

There are no planned interim analyses.

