## **3.1 STUDY DESIGN**

### **3.2 Description of Study Design**

In this randomized, bilateral, double-masked, 1-month study with two parallel groups, approximately 260 subjects (520 eyes) will be enrolled at approximately 10 investigative sites in the United States (US).

Approximately one-half of the subjects (130) will be randomized to receive Test contact lenses and the other half (130) will be randomized to receive Control contact lenses in a 1:1 ratio at the Dispensing Visit. All subjects will be dispensed study lenses according to a unique randomization schedule provided to each site. Both groups will wear the study lenses on a daily wear basis. After two weeks of wearing the study lenses, the subjects will return for an exam, and then continue wearing the same study lenses for the remaining 2 weeks.

Each subject will be required to complete four Take Home Lens Performance Surveys. All take home surveys are required to be completed after a minimum of 5 days of experience with the dispensed study lenses. The first two take home surveys must be returned at the 2-Week Follow-up Visit. The remaining two take home surveys are required to be completed during each of the remaining two weeks (one per week) and must be returned at the final 1-Month Follow-up Visit. All take home surveys will be reviewed by the Investigator for completeness when returned.

Subjects will be required to clean and disinfect their lenses each day using Biotrue™ multi-purpose solution and the contact lens cases provided. The lenses will be worn on a daily wear basis for the entire 1-month study with no scheduled replacement.

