#### 5.2.1 Screening Visit

**NOTE:** All VA measurements **MUST** be made using a phoropter.

After obtaining written informed consent, prospective subjects will be screened to determine whether they meet the entry criteria for the study.

Screening will proceed as follows:

- a. Enter the following information in the e-CRF :
  - subject initials
  - subject date of birth
  - screening date
- b. Collect demographic and baseline habitual lens information and record in the e-CRF:
  - The investigator or designees will ask and record the subject's responses to the Lens Performance Survey (100-point scales) regarding their experience with their habitual lens.
  - average daily wearing time
  - confirm current lens brand as Acuvue Oasys
  - current lens care products
  - habitual lens centration
  - habitual lens movement
- c. Perform the following baseline assessments (without lenses) and record in the

Study ROC2-17-014 - Protocol

e-CRF:

- spherocylindrical refraction
- distance best spectacle-corrected visual acuity (BSCVA)
- keratometry

Perform a slit lamp examination (remove the lenses if the subject wore their habitual lenses to the visit). Record the results and findings in the e-CRF.

- d. “Screen Fail” subjects are ineligible and cannot continue in the study. The reason for screen failure must be documented and maintained with a copy of their ICF.
- e. If the subject is found to be eligible, the Investigator may complete the Dispensing Visit on the same day as the Screening Visit.
- f. If lenses need to be ordered record the required information on the Material Reorder Form and schedule the subject for their Dispensing Visit on a separate day as instructed by the Sponsor.
- g. The following e-CRF should be completed.
  - Screening Visit

If the subject is discontinued or exited at this visit:

- Subject Exit

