### 5.2.2 Dispensing Visit

**NOTE:** All VA measurements **MUST** be made using a phoropter.

**NOTE:** Ensure all lenses/lens types for the subject have been received prior to the Dispensing Visit.

**NOTE:** The Investigator should allow the lenses to properly settle on the eye for a minimum of 5 minutes.

If the Dispensing Visit is occurring on a separate day from the Screening Visit, perform (a) and (b) below, otherwise if the Dispensing Visit occurs on the same day as the Screening Visit, skip to (c).

- a. Perform a slit lamp examination (remove the lenses if the subject wore lenses to the visit). Record the results and findings in the e-CRF.
- b. Reconfirm subject eligibility. If the subject continues to be eligible, continue the Dispensing Visit. If the subject is determined to be ineligible, they must be discontinued and the reason recorded on the Subject Exit Form.
- c. If the subject is eligible, the unmasked designee will dispense 1 pair of the study lenses according to the unique randomization schedule provided to each site. The subject **MUST** insert the lenses.

**NOTE:** Study lenses should be allowed to equilibrate a minimum of five minutes on the eye.

Record the following into the e-CRF:

- The Investigator or designees will ask and record the subject’s responses to the

Study ROC2-17-014 - Protocol

Lens Performance Survey (100-point scales).

- dispensed lens sphere power, type, and lot number
- distance lens VA
- over-refraction and distance VA
- lens wettability
- lens centration
- lens movement

For each eye, compare the high contrast distance lens VA to the high contrast BSCVA obtained previously in the Screening Visit. If the VA has decreased by 10 letters (0.2 logMAR) or more, explain.

- g. The Investigator must assess if the lens fit and VA is acceptable.

Remind the subjects to complete the first two Take Home Lens Performance surveys after a minimum of 5 days of experience with the study lenses for each week and to return the surveys at their next visit.

- h. Subjects who meet all inclusion criteria but are found not to be eligible to participate in the study due to lens fitting characteristics at the Dispensing Visit will be exited as a non-dispensed subject.
- i. The following e-CRFs should be completed.
- Dispensing Visit

If the subject is discontinued or exited at this visit:

- Subject Exit

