## **7.1 Statistical Methods**

### **7.2 Study Endpoints**

#### Primary Effectiveness Endpoints

- For each question on the take home questionnaire at each of four week-long intervals, the proportion of subjects providing a response in the top 3 boxes.
  - Note that these endpoints are not pass/fail criteria for the study. Rather, these are the most important data that will be evaluated.

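### The secondary comfort scores are tested without the Screening score or site: the tests are valid, but precision already paid for goes unused

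*Combined protocol and SAP*

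**What the plan says.** Section 7.2 lists the secondary effectiveness endpoints as "Lens performance survey (100 point scales) questions" and names three: comfort on insertion, overall comfort and comfort at the end of the day. Section 7.6 gives the comparison: "Two-sided two-sample t-tests will be used to compare the treatment groups by visit". It names no baseline term, no site term and no change from baseline, and it gives no reason for leaving them out.

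Two features of the design bear on that choice.

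- **A score before treatment.** At Screening (Section 5.2.1) subjects answer the "Lens Performance Survey (100-point scales) regarding their experience with their habitual lens". All subjects wear the same habitual brand. The survey is asked again at Dispensing, but with the study lenses already inserted (Section 5.2.2: "Study lenses should be allowed to equilibrate a minimum of five minutes on the eye"), and then at 2 weeks and 1 month.
- **Allocation by site.** Section 3.2: "All subjects will be dispensed study lenses according to a unique randomization schedule provided to each site". Section 7.4: "Within each site and overall, the number of subjects randomized to each treatment will be approximately balanced".

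The primary top-3 proportions are handled the same way. They "will be compared between treatments using chi-square tests by week", with no site term, and Section 7.2 adds: "Note that these endpoints are not pass/fail criteria for the study".

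**The concern.** The plan collects a pre-treatment rating from the same person, on the same survey and scale, and balances the lenses within site. It then ignores both when it compares comfort. Two separate effects follow.

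1. Leaving out the Screening score keeps the type I error correct. It loses precision to the extent that Screening and follow-up scores correlate.
2. Leaving out site, when allocation is balanced within site, makes the test slightly conservative if scores differ between sites. The t-test's standard error includes between-site variation that the design has already removed from the comparison.

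Neither effect produces false positives. What is at stake is missing a real comfort difference, or reporting it with a wider interval than necessary. Section 7.3 fixes 130 per group as the most the sponsor can afford, so extra precision has to come from data already collected.

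**Working it through.** **Inputs from the documents.** 130 subjects per group, two-sided 0.05, 80% power for 0.500 against 0.670 (Section 7.3); about 10 sites with about 26 subjects each (Section 3.4); 1:1 allocation balanced within site (Section 7.4).

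**Assumed inputs.** The documents give no SD for the comfort scores, no Screening/follow-up correlation *r* and no site ICC. Ranges starting at zero are used for *r* and the ICC, and differences are expressed in SD units.

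**The plan's own figure.** With the pooled-variance chi-square formula, the mean proportion is 0.585 and

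power = Φ{[0.170·√130 − 1.960·√(2·0.585·0.415)] / √(0.500·0.500 + 0.670·0.330)} = 0.798.

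The stated 80% reproduces. It concerns the primary endpoint; no power is stated for the comfort scores.

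**Comfort scores, t-test.** By the normal approximation the detectable difference is (1.960 + 0.842)·√(2/130) = 0.347 SD. With the exact t distribution on 258 degrees of freedom it is 0.349 SD.

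**Comfort scores, ANCOVA.** The Screening score multiplies the residual SD by √(1 − r²). With lens, one covariate and 10 sites, 260 − 12 = 248 degrees of freedom remain. With no site effect assumed:

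| Assumed r | Power at 0.349 SD | Detectable difference at 80% power | Equivalent n per group, 130/(1 − r²) |
|---|---|---|---|
| 0 | 80.0% | 0.349 SD | 130 |
| 0.2 | 81.6% | 0.342 SD | 135 |
| 0.3 | 83.6% | 0.333 SD | 143 |
| 0.5 | 89.9% | 0.302 SD | 173 |

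At r = 0 the ten degrees of freedom cost less than 0.1 power point.

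**Leaving out site.** With exact balance within site, the actual size of the nominal 0.05 t-test is about 2{1 − Φ[1.960/√(1 − ICC)]}. This gives 0.050, 0.044 and 0.039 for ICC 0, 0.05 and 0.10. In simulation (10 sites, 13 per arm per site, 20,000 runs per case) the t-test's size was 0.049–0.051, 0.043–0.046 and 0.038–0.040. ANCOVA with site stayed at 0.046–0.051 throughout.

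**Both together.** A separate simulation (3,000 runs per case, ICC 0 to 0.10) was run at the difference where the t-test has about 80% power. ANCOVA with site reached 82–87% at r = 0.3 and 91–92% at r = 0.5. At r = 0 and ICC 0 both methods gave 81%.

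**Primary proportions.** These were simulated at 0.500 against 0.670 with 40,000 runs per case, comparing the chi-square test with a site-stratified Cochran-Mantel-Haenszel (CMH) test. Size was checked at 0.585 in both arms.

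| Assumed between-site SD, log-odds | Chi-square power | CMH power | Chi-square size | CMH size |
|---|---|---|---|---|
| 0 | 80.2% | 80.2% | 0.050 | 0.050 |
| 0.3 | 80.7% | 80.9% | 0.051 | 0.052 |
| 0.5 | 80.9% | 81.9% | 0.045 | 0.049 |
| 0.8 | 82.0% | 84.6% | 0.038 | 0.050 |

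The gain is about 0, 0.2, 1.0 and 2.7 power points before rounding. The comfort-score gains above do not carry over to this endpoint.

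**The case against.** The strongest reply is that a prespecified t-test on randomized groups is legitimate, and that nothing in the protocol turns on a comfort p-value. Even the primary endpoints are not pass/fail, and there is no multiplicity adjustment. The benefit also rests wholly on assumed values. The Screening score rates a different lens; everyone wears the same brand; and people previously unsuccessful with either study lens are excluded. All of this could keep the correlation low, and at 0.2 the gain is only 1.6 power points. These points stand as limits on the weight of the finding. They do not make the unadjusted test the better choice, because adjustment costs almost nothing when the correlation is zero.

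Other points stand in part.

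- **Matching items.** Section 5.2.1 names the survey but lists no items, and the form is not in the text available. A survey of the same name and scale very probably has the same comfort items, but this should be confirmed.
- **Balance.** The size calculation assumes equal sites and exact balance. The protocol promises only approximate balance and allows enrollment to move between sites.
- **Primary endpoint.** Changing the primary test brings little, as the second table shows.
- **Unit of analysis.** Validity of the t-test assumes one score per subject. Section 7.6 speaks of eyes, while the survey records the subject's answers. If each score were entered once per eye, the nominal 0.05 test would run at 2{1 − Φ(1.960/√2)} = 0.166. That is a separate matter, but the wording should be settled in the same edit.

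**Conclusion.** The concern holds as a loss of efficiency on secondary endpoints; there is no bias and no inflation of type I error. With 130 per group, the gain at a difference of 0.349 SD runs from nothing at r = 0 to about 10 power points at r = 0.5. If sites differ at an ICC of 0.05 to 0.10, the t-test runs at about 0.044 to 0.039 instead of 0.05. These magnitudes depend on assumed correlations and ICCs, on roughly equal and balanced sites, on one score per subject, and on a Screening item that matches each comfort item. The direction does not depend on the particular values: adjustment is worth something when either the correlation or the site effect is present, and costs less than 0.1 power point when neither is. The change should be made, but the study's validity does not depend on it.

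**What to change.** Amend Section 7.6 before unmasking.

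- **Main comfort analysis.** For each score at the 2-week and 1-month visits, fit an ANCOVA with lens, the corresponding habitual-lens Screening score and site. Report the adjusted difference with its 95% CI.
- **Baseline.** Name the Screening score. The Dispensing score is recorded on the study lens and is an outcome. State how Dispensing scores will be compared: either the planned t-test or the same ANCOVA would do.
- **Small sites.** Prespecify a pooling rule; for example, any site with fewer than 5 analysed subjects in either arm joins the next smallest.
- **Missing Screening scores.** Report how many subjects lack one. Keep the t-test, which includes them, as a sensitivity analysis.
- **Unit.** Say that survey scores are analysed per subject.
- **Weekly top-3 proportions (lower priority).** Use a site-stratified CMH test with a stratified risk difference and 95% CI. Where counts are sparse, replace the present Fisher rule with an exact stratified test.

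The cost is wording only, with no new visits or data, once the survey form confirms that the Screening items match. Because the analysis text sits in the protocol, Section 8.7 requires IRB/EC approval of the amendment before it takes effect.
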